9.5.2.8 Potential Hy's Law Cases

Potential Hy's law criteria are:

- ALT or AST $\geq 3 \times$ ULN *AND*
- Total bilirubin $\geq 2 \times$ ULN *AND*
- Alkaline phosphatase $< 2 \times$ ULN

Study center personnel must report every patient who meets these potential criteria. Typically, all 3 analytes will be obtained from the same sample, but they may come from multiple samples taken within a 24-hour period. This requirement applies from the time he or she signs the ICF for the study until 30 days after the final protocol-defined study visit or the last known dose of investigational product (if the final visit does not occur).

A laboratory alert for potential Hy's laws cases will be in place and the laboratory must notify Investigators and AGN immediately when the above criteria have been met. A potential Hy's law case must be faxed to AGN on an AE of Special Interest Form as soon as possible (within 24 hours of learning of the potential Hy's law case) to the SAE/Pregnancy fax number stated in Section 9.5.2.6, even if no AE has occurred. The eCRF for potential Hy's law cases must be completed within 7 calendar days. Every effort to determine the cause of the liver enzyme abnormalities must be made, and close monitoring should be initiated in conjunction with the Study Physician and in accordance with the FDA "Guidance for Industry: Drug Induced Liver Injury- Pre-Marketing Clinical Evaluation" July 2009.

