Serum β-hCG:	Female patients of childbearing potential only. Will be performed at Visit 1 (Screening) and for randomized patients at Visit 8/ET. Urine pregnancy tests may be performed at the discretion of the Investigator at any visit during the double-blind treatment period; if negative, perform a serum β -hCG test to rule out pregnancy.
Other laboratory assessments may be repeated at any visit if there was an abnormal finding at the most recent, previous evaluation or if additional information is clinically necessary to appropriately evaluate the patient's current condition, follow up and/or manage an AE. Fasting for at least 8 hours is recommended before unscheduled visits to assess serum chemistry.	
A central laboratory will be used to evaluate all urine and blood samples, which will be collected, processed, and stored according to the instructions provided by the laboratory.	

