11.0 SAFETY ANALYSES

The safety analysis will be performed for the double-blind treatment period and the double-blind down-taper period (only for safety parameters collected during the double-blind down-taper period), separately, using the Safety Population unless stated otherwise.

The safety parameters will include adverse events (AEs) and clinical laboratory parameters, vital sign measurements, electrocardiographic (ECG) parameters, suicide risk assessment using the Columbia-Suicide Severity Rating Scale (C-SSRS), and growth evaluation. For each safety parameter, the last nonmissing safety assessment before the first dose of investigational product will be used as the baseline for all analyses of that safety parameter. Continuous variables will be summarized by number of patients and mean, SD, median, Q1, Q3, minimum, and maximum values. Categorical variables will be summarized by number and percentage of patients.

For patients who take the double-blind down-taper investigational product, the double-blind treatment period starts with the first dose of double-blind investigational product and ends with the last assessment date up to the first dose of the double-blind down-taper investigational product. The double-blind down-taper period starts one day after the end of the double-blind treatment period and ends with the latter of the last dose of the double-blind down-taper investigational product and the last assessment date.

For patients who do not take the double-blind down-taper investigational product, the double-blind treatment period starts with the first dose of double-blind investigational product and ends with the latter of the last dose of the double-blind investigational product and the last assessment date.

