11.2 CLINICAL LABORATORY PARAMETERS

Descriptive statistics for clinical laboratory values (in SI units) and changes from the baseline values at each assessment time point (including the end of the double-blind treatment period) will be presented by treatment group for the following laboratory parameters:

Hematology: Absolute and differential white blood cell count, erythrocyte count, hemoglobin, hematocrit, platelet count, and red blood cell indices (mean corpuscular volume, mean corpuscular hemoglobin, and mean corpuscular hemoglobin concentration)

Chemistry: Sodium, potassium, calcium, chloride, bicarbonate, glucose, blood urea nitrogen, creatinine, total protein, alkaline phosphatase, albumin, total bilirubin, direct bilirubin, indirect bilirubin, AST, ALT, Free T3, free T4, TSH, lactate dehydrogenase, creatine phosphokinase, γ -glutamyl transpeptidase, uric acid, phosphate, lipid panel (total cholesterol, triglycerides, low density lipoproteins, high density lipoproteins), prolactin, insulin, and magnesium

Urinalysis: Specific gravity, pH, protein, glucose

In addition, descriptive statistics for values and changes from the baseline values in conventional units at each assessment time point will be presented for selected clinical laboratory parameters listed in Appendix II.

Clinical laboratory test values will be considered potentially clinically significant (PCS) if they meet either the lower-limit or higher-limit PCS criteria listed in Table 11–1. The number and percentage of patients who have PCS postbaseline clinical laboratory values will be tabulated by treatment group. The percentages will be calculated relative to the number of patients with available non-PCS baseline values and at least 1 postbaseline assessment. The numerator will be the total number of patients with available non-PCS baseline values and at least 1 PCS postbaseline value. A supportive listing of patients with PCS postbaseline values will be provided, including the patient identification (PID) number, and baseline and all postbaseline (including non-PCS) values. In addition, a listing of all AEs that occurred in patients who had PCS postbaseline clinical laboratory values will be provided.

Table 11–1 Criteria for Potentially Clinically Significant Laboratory Values

Parameter	SI Unit	Lower Limit	Higher Limit
HEMATOLOGY			
Basophils	%		> 6
Eosinophils	%		> 10
Hematocrit	ratio	< 0.9 × LLN	_
Hemoglobin	g/L	< 0.9 × LLN	_
Lymphocytes	%	< 10	> 60
Monocytes	%	_	> 20

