Neutrophils	%	< 30	> 90
Platelet count	$\times 10^9/L$	≤ 75	≥ 700
White blood cell count	$\times 10^9/L$	≤ 2.5	≥ 15
CHEMISTRY			
Albumin	g/L	< 0.9 × LLN	> 1.1 × ULN
Alkaline phosphatase	U/L	_	\geq 3 × ULN
Alanine aminotransferase	U/L	_	\geq 3 × ULN
Aspartate aminotransferase	U/L	_	\geq 3 × ULN
Bicarbonate	mmol/L	< 0.9 × LLN	> 1.1 × ULN
Blood urea nitrogen	mmol/L	_	> 1.2 × ULN
Calcium	mmol/L	< 0.9 × LLN	> 1.1 × ULN
Chloride	mmol/L	< 0.9 × LLN	> 1.1 × ULN
Cholesterol, total	mmol/L	_	> 1.3 × ULN
Creatinine	μmol/L	_	> 1.3 × ULN
Glucose	mmol/L	< 0.8 × LLN	> 1.4 × ULN
High-density lipoprotein	mmol/L	< 0.8 × LLN	_
Low-density lipoprotein	mmol/L	_	> 2.0 × ULN
Magnesium	mmol/L	< 0.9 × LLN	> 1.1 × ULN
Phosphate	mmol/L	< 0.9 × LLN	> 1.1 × ULN
Potassium	mmol/L	< 1.0 × LLN	> 1.0 × ULN
Sodium	mmol/L	< 1.0 × LLN	> 1.0 × ULN
Total bilirubin	μmol/L	_	> 1.5 × ULN
Total protein	g/L	< 0.9 × LLN	> 1.1 × ULN
Triglyceride	mmol/L	_	> 3.0 × ULN
URINALYSIS			•
Protein	mg/dL	_	at least 2 +
Glucose	mmol/L	_	at least 2 +
		·	•

ALT = alanine aminotransferase; AST = aspartate aminotransferase; CPK = creatine phosphokinase; LLN = lower limit of normal value provided by the laboratory; PCS = potentially clinically significant; SI = Le Système International d'Unités (International System of Units); ULN = upper limit of normal value provided by the laboratory.

Shift tables from baseline to end of double-blind treatment period for clinical laboratory parameters will be presented by treatment group for the following categories: low, normal, and high.

Potential Hy's Law criteria is defined by a postbaseline elevation of alanine aminotransferase (ALT) or aspartate aminotransferase (AST) \geq 3x ULN (ULN = upper limit of normal laboratory reference range), along with total bilirubin (TBL) \geq 2x ULN and a non-elevated alkaline phosphatase (ALP) < 2x ULN, all based on blood draws collected within a 24-hour period. The number and percentage of patients who meet the following criteria of clinical interest during the double-blind treatment period will be tabulated by treatment group. A supportive list will also be provided.

- ALT: $\geq 3x$ ULN, $\geq 5x$ ULN, $\geq 10x$ ULN, $\geq 20x$ ULN
- AST: $\geq 3x$ ULN, $\geq 5x$ ULN, $\geq 10x$ ULN, $\geq 20x$ ULN
- ALT or AST: $\geq 3x$ ULN, $\geq 5x$ ULN, $\geq 10x$ ULN, $\geq 20x$ ULN
- TBL: $\geq 2x$ ULN
- ALP: $\geq 1.5 x ULN$

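### For patients who take down-taper product, the SAP's Hy's law and liver-enzyme table omits criteria first met after the first taper dose, although the protocol still collects those cases

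*Protocol*

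**What the plan says.** **Collection.** Protocol 9.5.2.8 has sites report every patient meeting the potential Hy's law criteria from consent "until 30 days after the final protocol-defined study visit or the last known dose of investigational product", the last dose applying when the final visit does not take place. Reporting is required whether or not there is an adverse event, and a dedicated eCRF is completed.

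**Analysis.** SAP 11.2 sets out rows for ALT, AST, bilirubin and ALP thresholds and for concurrent elevations, including the Hy's law composite. It says that patients "who meet the following criteria of clinical interest during the double-blind treatment period will be tabulated by treatment group".

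**Period.** SAP 11.0 ends that period in two ways. For patients who take taper product it "ends with the last assessment date up to the first dose of the double-blind down-taper investigational product". For patients who do not, it "ends with the latter of the last dose of the double-blind investigational product and the last assessment date".

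**Draws.** In the schedules of both documents, clinical laboratory tests appear once after baseline, at Visit 8/ET. Visit 9 has none. Protocol 9.5.2.9 adds: "Other laboratory assessments may be repeated at any visit if there was an abnormal finding at the most recent, previous evaluation".

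**The concern.** The table's cut-off falls just after the only scheduled postbaseline chemistry draw. A central laboratory evaluates the samples, so an abnormal Visit 8 result would usually be known, and repeated, after the visit. By then a patient who tapers will often have taken the first taper dose. If Visit 8 is remote and taper product is couriered, even the scheduled draw could come after that dose.

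Two things are at stake. A potential Hy's law case that the sponsor holds on its own eCRF could be missing from the by-arm count of such cases. And the length of time over which a patient can be counted depends on whether the patient tapers. Protocol 9.1 and 9.4.5.3 leave that to the Investigator's judgement after randomization.

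**Working it through.** The plan gives no figure to reproduce, so the check compares the texts and adds simple day arithmetic.

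1. **Same finding, two patients (hypothetical).** Both have Visit 8 on Day 57, the nominal day in SAP Table 16–1, with ALT at least 3 × ULN and normal bilirubin. A repeat on Day 62 shows ALT still at least 3 × ULN, bilirubin at least 2 × ULN and ALP below 2 × ULN. Both documents require the composite to come from samples within 24 hours, so the Day 57 ALT cannot be paired with the Day 62 bilirubin. The case is dated to Day 62.
   - Patient A took the first taper dose on Day 58. The treatment period ended on Day 57, and Day 62 belongs to the down-taper period. A is counted in the ALT row but not in the bilirubin or Hy's law rows.
   - Patient B took no taper product. The treatment period runs to the last assessment, which is at least Day 62. B is counted in all of these rows.

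2. **Length of the uncounted interval for a tapering completer.**
   - Visit 8: Day 57.
   - Visit 9: 57 + 7 = Day 64.
   - Protocol window closes: 64 + 30 = Day 94.
   - Interval: 94 − 57 = 37 days, 7 of them nominally on taper product.
   - With Visit 9 at 1 week ± 3 days after Visit 8: 34 to 40 days.

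3. **Does the general rule in SAP 11.0 extend the table?** SAP 11.0 analyses the two periods separately, the down-taper period "only for safety parameters collected during the double-blind down-taper period". No chemistry is scheduled in the taper, and the specific sentence in SAP 11.2 names the treatment period alone. By contrast, SAP 11.1, 11.3 and 11.5.1 name the taper period explicitly for TEAEs, vital signs and C-SSRS.

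4. **Can other outputs show a case like A's?**
   - *Laboratory PCS table.* SAP 11.2 says: "The number and percentage of patients who have PCS postbaseline clinical laboratory values will be tabulated by treatment group". No period is given, and SAP 16.4 uses all postbaseline assessments for PCS values. Its liver limits are ALT, AST and ALP at least 3 × ULN and bilirubin above 1.5 × ULN. It can show single-analyte elevations but not the composite. The title of this table in SAP Appendix III restricts it to the treatment period, so its own window is unclear.
   - *TEAE tables.* They run to 30 days after the last dose, but the case need not be an adverse event. Protocol 9.5.2.5 enters poststudy events in the eCRF only if they are serious or judged potentially related.
   - *Listings.* SAP 16.4 lists all assessments, but a listing is not a by-arm count.

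5. **Scale of one case, for illustration only.** With the planned 160 per arm, 0/160 has an exact upper 95% limit of 1 − 0.025^(1/160) = 2.3%, and 1/160 = 0.6%. This shows how much one case weighs. It does not estimate how many would be missed.

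**The case against.** The strongest reply is that a reporting duty is not an analysis window. Protocol 9.5.2.8 governs what sites tell the sponsor, from consent onward. The protocol's laboratory analysis section (9.7.6.2) has no Hy's law table and no 30-day follow-up. The SAP adds a display and need not match the reporting period. That stands: there is no contradiction between the documents. It does not explain why equivalent late draws count for patients who skip the taper and not for those who take it.

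Several stronger readings are tempting, and the documents do not support them:

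- *Late cases reach no table at all.* As shown above, single-analyte values may reach the PCS table, cases recorded as adverse events may reach the TEAE tables, and non-tapering patients' later draws are in the liver table.
- *Every repeat of an abnormal Visit 8 result is lost.* A Visit 8 value already over a threshold is counted for that threshold, and repeats before the first taper dose are inside the period. Only a criterion newly met later is missed.
- *About 40% of the safety data is uncounted.* The 37 days are calendar time with no scheduled chemistry, and 30 of them are nominally off drug. The gap concerns unscheduled, repeat or delayed draws.
- *Rates are diluted by untested patients.* SAP 11.2 states no denominator for these rows. The Safety Population is a possible default, but table specifications are in a separate document, so this is inference.

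**Conclusion.** The concern holds for the liver table and for patients who take taper product. Read exactly, SAP 11.0 and 11.2 leave out any liver criterion first met after the first taper dose, while counting the equivalent finding in a patient who does not taper. The composite has no other by-arm summary in the SAP.

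The uncounted interval is nominally 37 days, but the number of cases lost cannot be computed: the documents give no liver-event rate, no rate of repeat draws and no expected taper uptake by arm. A reader might infer that the table favours levomilnacipran. Nothing in the documents supports a direction; if taper uptake is similar across arms, the effect is mainly an undercount in all of them.

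The conclusion assumes that the SAP's period definitions apply to the liver rows as written, and that the separate table specifications do not override them. It is worth correcting before unblinding because one case matters for so rare an outcome and the needed data are already collected.

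**What to change.** In SAP 11.2, tabulate the ALT, AST, bilirubin, ALP and potential Hy's law criteria by arm from the first dose to 30 days after the final protocol-defined visit, or after the last dose if there is no final visit. In addition:

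- Use all scheduled and unscheduled postbaseline draws.
- Show separate rows for treatment, down-taper and follow-up. SAP 11.0 runs the down-taper period to the last assessment, so follow-up needs its own start, and late draws in non-tapering patients should go in the follow-up row.
- State the denominator as patients with at least one postbaseline draw, in line with the PCS table's requirement for a postbaseline assessment.
- Settle the period of the laboratory PCS table so that SAP 11.2, SAP 16.4 and the Appendix III title agree.

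The cost is a wording change and a few more table rows, with no new data collection. The longer window adds mostly off-drug time, which the separate rows keep distinguishable from treatment.

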9.5.2.9 Clinical Laboratory Determinations

Blood and urine samples for clinical laboratory tests will be collected as detailed in the [Schedule of Evaluations](#) (Section 2.0). During Screening, the Investigator will assess the clinical significance of any values that are outside the reference ranges provided by the central laboratory; patients with abnormalities judged to be clinically significant will be excluded from the study.

Patients will be instructed to fast overnight (for at least 8 hours) before coming in for their appointments when clinical laboratory blood tests are to be drawn. If non-fasting, an attempt should be made to draw blood at least 4 hours after a meal.

A UDS will be conducted for all patients at Visit 1 (Screening). A negative UDS for prohibited substances (illegal drugs or prohibited concomitant medications [see [Appendix III](#) and Exclusion Criterion #18]) is required before Visit 2 (Baseline) for the patient to continue in the study. Amphetamines can be allowed if prescribed for treatment of attention deficit disorder at a dose that is stable for at least 60 days before Visit 1 (Screening). If not stable for at least 60 days before Visit 1 (Screening), the patient should be discontinued. However, the patient can be rescreened on a later date.

Patients who have a positive UDS at Visit 1 (Screening) for other prohibited substances (barbiturates, benzodiazepines, opiates, cannabinoids, cocaine, methadone, phencyclidine, or other prohibited concomitant medications) may be allowed to enroll if (1) there is no suspicion of drug abuse per the Investigator judgment, (2) the use is discontinued and (3) this is documented by a negative UDS before Visit 2 (Baseline). If the repeat test cannot be performed within 21 days, the patient should be discontinued from the study. The patient can be rescreened on a later date and must have a negative UDS to be considered for inclusion in the study.

Alcohol consumption is prohibited during the study. A UDS or blood alcohol test may be performed at any time during the study at the discretion of the Investigator. A patient with a positive blood alcohol test or a positive UDS for any prohibited substances at any postrandomization visit may be allowed to continue in the study if approved by the Investigator and by the Study Physician.

Females of childbearing potential will be required to have a serum β -hCG pregnancy test at Visit 1 (Screening) and Visit 8/ET. Positive pregnancy test results at Visit 1 will exclude female patients from participating in the study. At every study visit, Investigators should inquire about the use of acceptable methods of contraception in females of childbearing potential who are, or become, sexually active, and perform a urine pregnancy test if there is any question of non-compliance with contraception. If the urine pregnancy test is negative, a serum β -hCG pregnancy test must be performed to rule out pregnancy. Any positive pregnancy test results during the study will result in patient termination from the study.

The following clinical laboratory levels will be measured:

Hematology:	Absolute and differential white blood cell count, erythrocyte count, hemoglobin, hematocrit, platelet count, and red blood cell indices (mean corpuscular volume, mean corpuscular hemoglobin, and mean corpuscular hemoglobin concentration)
--------------------	---

Chemistry:	Sodium, potassium, calcium, chloride, bicarbonate, magnesium, phosphate, glucose, blood urea nitrogen, creatinine, total protein, alkaline phosphatase, albumin, bilirubin (total; direct; indirect), AST, ALT, total cholesterol, low-density lipoprotein, high-density lipoprotein, triglycerides
Urinalysis:	Specific gravity, pH, protein, glucose, ketones, nitrite, bilirubin, and blood
Thyroid:	Free thyroxine and thyroid stimulating hormone (TSH) tests at Visit 1 (Screening)
Hepatitis screening:	Hepatitis-C virus antibody, hepatitis-B surface antigen, and hepatitis-B core antibody total will be tested. Reflex hepatitis-B core antibody IgM will be performed for all hepatitis-B core antibody total positive or reactive results. Hepatitis screening will be conducted at Visit 1 (Screening)
UDS:	Benzoylecgone (cocaine), barbiturates, amphetamines, benzodiazepines, cannabinoids, opiates, methadone, phencyclidine. UDS will be performed for all patients at Visit 1 (Screening). UDS may be repeated during the study at the Investigator's discretion
Blood alcohol level:	Blood alcohol level will be conducted at Visit 1 (Screening). May be performed at random during the study upon request of the Investigator
Serum β-hCG:	Female patients of childbearing potential only. Will be performed at Visit 1 (Screening) and for randomized patients at Visit 8/ET. Urine pregnancy tests may be performed at the discretion of the Investigator at any visit during the double-blind treatment period; if negative, perform a serum β -hCG test to rule out pregnancy.
Other laboratory assessments may be repeated at any visit if there was an abnormal finding at the most recent, previous evaluation or if additional information is clinically necessary to appropriately evaluate the patient's current condition, follow up and/or manage an AE. Fasting for at least 8 hours is recommended before unscheduled visits to assess serum chemistry.	
A central laboratory will be used to evaluate all urine and blood samples, which will be collected, processed, and stored according to the instructions provided by the laboratory.	

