The incidence of common ($\geq 2\%$ of patients in any treatment group) TEAEs during the double-blind treatment period will be summarized separately by preferred term and treatment group and will be sorted by decreasing frequency for the test treatment. In addition, the incidence of fatal on-therapy SAEs (ie, events that caused death) will be summarized separately by treatment group and preferred term. An SAE will be defined as an on-therapy SAE if it occurred on or after the date of the first dose of double-blind investigational product and within 30 days of the date of the last dose of double-blind investigational product.

The incidence of SAEs and AEs leading to premature discontinuation of the study will also be summarized by study period, system organ class, preferred term, and treatment group.

Listings will be presented for SAEs, AEs leading to discontinuation, and death (if any).

9.7.6.2 *Clinical Laboratory Parameters*

Descriptive statistics for clinical laboratory values (in SI units) and changes from the baseline values at each assessment time point will be presented by treatment group for each clinical laboratory parameter.

The number and percentage of patients with potentially clinically significant (PCS) postbaseline clinical laboratory values will be tabulated by treatment group. The criteria for PCS laboratory values will be detailed in the Statistical Analysis Plan. The percentages will be calculated relative to the number of patients with available non-PCS baseline values and at least 1 postbaseline assessment. The numerator will be the total number of patients with available non-PCS baseline values and at least 1 PCS postbaseline value. A supportive listing of patients with PCS postbaseline values will be provided, including the PID number, study center number, and baseline and postbaseline values.

9.7.6.3 *Vital Signs*

Descriptive statistics for vital signs (ie, pulse rate, systolic and diastolic BP, and body weight) and changes from baseline values at each visit and at end of study will be presented by treatment group. In addition, height and weight z-scores will be calculated based on growth charts (see Section 9.7.6.5.2).

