16.10 CHARACTER VALUES OF CLINICAL LABORATORY PARAMETERS

If the reported value of a clinical laboratory parameter cannot be used in a statistical summary table because, for example, a character string is reported for a parameter of the numeric type, a coded value must be appropriately determined for use in the statistical analyses. The actual values, however, as reported in the database will be presented in the data listings.

Table 16–3 shows examples of how some possible laboratory results should be coded for the analysis.

Table 16–3. Examples of Coding Special Character Values for Clinical Laboratory Parameters

Laboratory Test, SI Unit	Possible Laboratory Results	Coded Value for Analysis
CHEMISTRY	1 0551616 Euroratory Results	Coded value for ringing
ALT, U/L	< 5	5
AST, U/L	< 5	5
Bilirubin, total, μmol/L	< 2	2
URINALYSIS		
	< 2.775, Negative	0
	[2.775, 5.55)	1+
C1 1/5	[5.55, 13.875)	2+
Glucose, mmol/L	[13.875, 27.75)	3+
	[27.75, 55.5)	4+
	≥55.5	5+
1/1	$> 0.444, \ge 0.444, > 0$, Trace	Positive
Ketones, mmol/L	≤ 0, Negative	Negative
II	> 8.0, ≥ 8.0	8.0
pH	≥ 8.5	8.5
	< 0, Negative	Negative
	[0, 0.15), Trace	0
Dustain a/I	[0.15, 0.3)	1+
Protein g/L	[0.3, 1.0)	2+
	[1.0, 5.0)	3+
	≥ 5.0	4+

ALT = alanine aminotransferase; AST = aspartate aminotransferase; SI = *Le Système International d'Unités* (International System of Units).

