18.0 CHANGES TO ANALYSES SPECIFIED IN PROTOCOL

None.

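### The laboratory list in SAP 11.2 does not match the panel in Protocol 9.5.2.9: four collected urine tests are left out, nine blood analytes lack scheduled post-baseline data, and SAP 18.0 declares no change.

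*Protocol*

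**What the plan says.** **Protocol.** Section 9.5.2.9 lists the urinalysis panel as "Specific gravity, pH, protein, glucose, ketones, nitrite, bilirubin, and blood". Its chemistry panel begins "Sodium, potassium, calcium, chloride, bicarbonate, magnesium, phosphate, glucose, blood urea nitrogen, creatinine, total protein, alkaline phosphatase, albumin" and continues with bilirubin (three fractions), AST, ALT and four lipids. Free thyroxine and TSH form a separate thyroid entry tied to Visit 1, and the Schedule of Evaluations in Section 2.0 marks them at that visit only. Sections 9.5.5.1 and 9.5.5.6 have urine and blood collected at Visit 1 and again at Visit 8/ET. Section 9.7.6.2 states that descriptive statistics for values and changes from baseline "will be presented by treatment group for each clinical laboratory parameter".

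**SAP.** Section 11.2 ties the descriptive statistics to a named list. The urine entry is "Urinalysis: Specific gravity, pH, protein, glucose". The chemistry entry includes "Free T3, free T4, TSH, lactate dehydrogenase, creatine phosphokinase", and further on GGT, uric acid, prolactin and insulin. Appendix II repeats creatine kinase, insulin and uric acid for tables in conventional units. Table 16-3, which sets coded values for analysis, has a row for "Ketones, mmol/L" with positive and negative codes. Section 18.0, headed "CHANGES TO ANALYSES SPECIFIED IN PROTOCOL", says there are none.

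**The concern.** The list in SAP 11.2 is operative text, because a programmer builds the laboratory tables from it. Followed as written, it has two effects.

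- Half of the urinalysis panel gets no by-arm descriptive summary, although the samples are taken from children before and after treatment and the protocol promises a summary for each parameter.
- Nine blood analytes get change-from-baseline rows for which the protocol schedules no post-baseline sample. A reader of the study report could not tell whether those rows were empty because the tests were missed or because they were never intended.

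The SAP also disagrees with itself, since it codes ketones for an analysis that 11.2 does not plan. Because SAP 18.0 reports no changes, nothing shows whether the differences are deliberate.

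**Working it through.** The plan gives no figure to reproduce. The check is an item-by-item comparison of the two lists, followed by a check of the visit schedule.

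**Urinalysis (Protocol 9.5.2.9 against SAP 11.2)**

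| Test | Protocol | SAP 11.2 |
|---|---|---|
| Specific gravity, pH, protein, glucose | yes | yes |
| Ketones | yes | no (but coded in Table 16-3) |
| Nitrite, bilirubin, blood | yes | no |

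8 protocol tests - 4 SAP tests = 4 omitted.

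**Chemistry**

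- Protocol: 13 analytes from sodium to albumin + 3 bilirubin fractions + AST and ALT + 4 lipids = 22.
- SAP 11.2: 31 analytes. All 22 protocol analytes are among them, so nothing is dropped on the chemistry side.
- Extra in the SAP: 31 - 22 = 9.
- In no protocol panel (7): free T3, LDH, CPK, GGT, uric acid, prolactin, insulin.
- In the protocol's thyroid entry, scheduled at Visit 1 only (2): free T4, TSH.

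**Size of the urine omission after treatment starts**

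- Inputs: 4 tests, one scheduled post-baseline urine sample (Visit 8/ET), and 480 planned patients (Protocol 9.1, SAP 4.0).
- Ceiling: 4 x 1 x 480 = 1,920 results.
- Illustration: apply the 17% dropout assumed in Protocol 9.7.9 and suppose that no patient who drops out gives an early-termination sample. Then 1,920 x (1 - 0.17) = 1,593.6, or about 1,594. The true count also depends on missed samples among completers.

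**Whether other SAP outputs cover the four urine tests**

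- Shift tables (SAP 11.2): these are by arm and refer to laboratory parameters without naming them. The categories are low, normal and high, which do not fit a negative/positive result. Coverage is unclear.
- Listings (SAP 16.4): all assessments are listed, so the results would be visible patient by patient.
- PCS counts (Table 11-1): the urine rows are protein and glucose only.

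**Reach of the nine extra analytes**

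None has a PCS row in Table 11-1, although CPK is defined in that table's footnote. None is part of the potential Hy's law criteria. The mismatch therefore touches descriptive, change-from-baseline and shift output only.

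**The case against.** The strongest reply is that this is list housekeeping with several backstops. Much of that stands.

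- **A drug effect on the four urine tests would be hidden.** A reader might infer this, but the documents do not support it. The results are listed under SAP 16.4. The shift-table wording does not expressly exclude them. Laboratory values that the investigator judges clinically significant are adverse events under Protocol 9.5.2.1, and treatment-emergent events are tabulated by arm under SAP 11.1. What is missing is an assured by-arm summary, not the data.
- **The nine analytes can have no post-baseline value.** This is too strong. Protocol 9.5.2.9 permits unscheduled repeats after an abnormal result or where clinically needed, so a TSH or free T4 repeat is possible. Such repeats cannot supply a systematic by-arm change table, so the accurate statement is that no post-baseline draw is scheduled.
- **The missing PCS rows are a further departure.** They are not. Protocol 9.7.6.2 leaves the PCS criteria to the SAP, and Table 11-1 also has no row for erythrocyte count, red cell indices, urine pH or specific gravity.
- **The sponsor relies on CPK, GGT or prolactin.** Nothing in either document does so.
- **The number of results at stake should count both visits.** That would double 1,920 to 3,840, but half of those are Visit 1 values taken before treatment.
- **The SAP list must be the one in error.** The central laboratory's actual panel is not in the documents. If it reports the extra analytes, deleting them would discard real data.

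SAP 4.0 also places table specifications in a separate document, which may resolve some of this. That document was not available for this review, and it would not remove the conflict between the protocol and SAP 11.2.

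**Conclusion.** The mismatch is real, undeclared and minor. Four of the eight urine tests that the protocol collects are outside the by-arm descriptive summaries that Protocol 9.7.6.2 promises. Nine of the 31 chemistry analytes in SAP 11.2 have no scheduled post-baseline draw, and seven of those nine appear in no protocol panel.

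The consequence is limited to descriptive safety reporting. Efficacy, power and type I error are untouched. At most 1,920 post-baseline urine results are affected; that ceiling assumes full enrolment and a complete Visit 8/ET sample from every patient. The conclusion rests on reading the list in SAP 11.2 as closed, which its wording indicates, and on taking Protocol 9.5.2.9 as the record of what is measured.

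**What to change.** 1. In SAP 11.2, add urine ketones, nitrite, bilirubin and blood as categorical by-arm summaries (for example negative/positive) from baseline to the end of double-blind treatment. SAP 11.0 already summarises categorical variables by number and percentage, so this needs no new method.
2. Reconcile the nine extra analytes with Protocol 9.5.2.9 and the central laboratory panel. Remove those not collected from SAP 11.2 and, for creatine kinase, insulin and uric acid, from Appendix II. Show free T4 and TSH at screening only. If any of the nine are in fact collected after baseline, correct the protocol panel instead.
3. Record any departure that remains in SAP 18.0.

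The cost is a SAP wording change and about one additional table. No new samples are needed, and study conduct does not change.
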